**2. SYNOPSIS**

Study Title	Cerebral Haemodynamic Changes During Cognitive Testing: A Functional Transcranial Doppler (fTCD) study
Internal ref. no.	
Trial Design	Prospective, observational, case-control study
Trial Participants	Healthy Control Subjects, Patients with Mild Cognitive Impairment, Patients with Vascular Dementia and Patients with Alzheimer’s Dementia
Planned Sample Size	11 Healthy Control Patients, 11 Patients with Mild Cognitive Impairment, 11 Patients with Vascular Dementia and 11 Patients with Alzheimer’s Dementia
Follow-up duration	None
Planned Trial Period	7 Months
Primary Objective	To compare the beat-to beat cerebral blood flow velocity (CBFv) between patients with Mild Cognitive Impairment (MCI), patients with Vascular Dementia (VascD), patients with Alzheimer’s Dementia (AlzD) and age-, gender- and blood pressure (BP)-matched healthy control (HC) subjects during performance of the Addenbrooke’s Cognitive III (ACE-III) examination
Secondary Objectives	
 
1) To investigate whether performance of the Addenbrooke’s Cognitive III Examination is associated with differences in other beat-to-beat cerebral haemodynamic parameters, specifically autoregulation index (ARI), between MCI patients, VascD patients, AlzD patients, and age-, gender- and BP-matched HC subjects.
 
2) To assess the acceptability and feasibility of this protocol in patients with cognitive impairment in clinical practice.
 
3) To assess the reproducibility of measurements in cognitively impaired patient group at 3 months from initial measurement
 

Outcome Measure	
This is not an intervention study, and therefore it would not be appropriate to assess the classical primary and secondary outcome measures such as death and disability for this study. However, we intend to evaluate the following relevant outcomes:
 
 
1. The percentage of recruited subjects (HC, MCI patients, VascD patients and AlzD patients) able to comply with the full measurement protocol.
 
2. The percentage of measurements rejected because of aspects related to data quality during the analysis protocol, with recorded reasons.
 
3. Overall, the percentage of recruited subjects (healthy controls, MCI patients, VascD patients and AlzD patients) in whom values for the following parameters can be derived:
 

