Cerebral haemodynamics can be studied using techniques such as functional magnetic resonance imaging (fMRI), positron emission tomography (PET) or single-photon emission computed tomography (SPECT). However, these techniques are expensive, in the case of SPECT involve radiation, and there are feasibility issues which are particularly problematic for older populations, including the need to lie still for prolonged periods and to have no metal implants. Transcranial Doppler Ultrasonography (TCD) is a simple, non-invasive imaging modality with high temporal resolution which allows for continuous and bilateral recording of cerebral blood flow velocity (CBFv) through the major cerebral arteries [Aaslid et al, 1982]. Measurements can be taken at rest, or during brain activation tasks such as sensorimotor functions or cognitive tasks. TCD measurement performed during such brain activation tasks is commonly referred to as functional TCD (fTCD), and is the assessment of blood flow in response to a specific cognitive stimulus or mental operation, a concept known as neurovascular coupling (NVC). Although the exact mechanisms of NVC continue to be explored and evaluated, it is thought that cerebral activation triggers a haemodynamic response involving neurons, astrocytes, vascular cells and local metabolites [Carmignoto et al 2010, Girouard et al 2006]. Cerebral blood flow (CBF) is also strongly influenced by the arterial partial pressure of carbon dioxide (PaCO2) which also modulates the effectiveness of cerebral autoregulation (CA), defined as the ability of the brain to maintain a relatively constant CBF in response to significant changes in cerebral perfusion pressure (CPP). CA is improved by hypocapnia and impaired by hypercapnia [Aaslid et al 1989, Paulson et al 1990]. It has been shown that CA can be reliably assessed by evaluating CBF responses to changes in PaCO2, such as those induced by hypo- and hyperventilation respectively [Dineen et al, 2010]. This concept is known as assessing vasomotor (or CO2) reactivity (VMR).

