The time domain approach in TFA is used to extract information about the CA mechanism from the analysis of mean BP, CBFv, heart rate (HR) and end-tidal partial pressure of carbon dioxide (EtCO2) with respect to time. In 1995 Tiecks et al derived a set of equations and curves based on the CBFv response to a sudden fall in induced by thigh cuff deflation. These equations and curves allow for the calculation of an autoregulatory index (ARI) from 0 to 9, where 0 represents absence of autoregulation i.e. CBF dependent on CPP, (a 'pressure-passive relationship') and 9 represents best measurable autoregulation. 'Normal' autoregulation is represented by an ARI of  $5 \pm 1$ . Other parameters obtainable in the time domain may also provide useful information regarding the integrity of dCA, including CrCP and RAP. CrCP is expressed in mmHg and is defined as the arterial pressure below which small vessels collapse and forward blood flow becomes zero, which in the cerebral circulation is equivalent to the sum of ICP and the contributions of vascular smooth muscle tone [Panerai 2003]. RAP is expressed in mmHg.s/cm and is an index of cerebrovascular resistance, which is equal to the total cerebrovascular resistance x cross-sectional area of the vessel [Evans et al 1988].

A meta-analysis of twelve TCD studies in AlzD and VascD [Sabayan et al 2012], reported significantly lower CBFv in patients with AlzD and VascD in comparison to healthy control subjects. CBFv was especially low in patients with VascD. In MCI, although there are limited data available, no significant differences in CBFv have been observed between MCI patients and healthy controls, unless restricting to amnesic MCI [Keage et al 2012].

Four studies which have used fTCD to investigate cerebral haemodynamic responses to brain activation in patients with dementia have reported conflicting findings; two found that individuals with AlzD had attenuated blood flow responses to cognitive demand, and two found no differences between dementia patients and controls. These studies used visual stimulation [Asil et al 2005, Gucuyener et al 2010, Rosengarten et al 2001], and a whispered verbal task, a thumb opposition task and a design discrimination task [Matteis et al 1998].

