## **11. STATISTICS**

### **11.1 Statistical analysis**

The null hypothesis being tested is that:

- (a) cerebral haemodynamic parameters, including CBFv and ARI, and any alterations related to the performance of the ACE-III Cognitive Examination are not significantly different between MCI, VascD, AlzD patients and HC subjects.

All normally distributed continuous variables will be described as mean (SD) and continuous variables with skewness as median (IQR). Comparison between baseline data for MCI patients, VascD patients, AlzD patients and HC will be made using Student t-tests for normally distributed data, or by appropriate non-parametric test, with Bonferroni correction applied to multiple comparisons. Repeated measures ANOVA will be adopted to test for the effect of performance of the ACE-III Cognitive Examination on CBFv and ARI between MCI patients, VascD patients, AlzD patients and HC subjects.

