### **11.2 Sample size calculation**

A formal sample size calculation was not possible for this study therefore a realistic number of participants has been selected based on previous experience of similar research studies by [name], [name] and [name].

However, to detect a change of 2 units in autoregulation Index (ARI) and to calculate the required sample size we followed the technique as previously described by others (Brodie FG et al, 2009). For this study a sample of 11 patients per intervention group will allow the detection of a difference between groups (MCI patients, VascD patients, AlzD patients and HC subjects) in the ARI of 2 units with 80% power at the 5% significance level.

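### Section 11.1 compares four non-randomised groups with no covariate; age and sex adjustment should be pre-specified, with task-related EtCO2 and BP change as a supplementary analysis

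*Combined protocol and SAP*

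**What the plan says.** Section 11.1 is the whole analysis plan. Its null hypothesis is that the haemodynamic parameters and "any alterations related to the performance of the ACE-III Cognitive Examination are not significantly different between MCI, VascD, AlzD patients and HC subjects". Two analyses follow:

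- Baseline: "Comparison between baseline data for MCI patients, VascD patients, AlzD patients and HC will be made using Student t-tests for normally distributed data", or a suitable non-parametric test, with Bonferroni correction.
- ACE-III effect: "Repeated measures ANOVA will be adopted to test for the effect of performance of the ACE-III Cognitive Examination on CBFv and ARI" across the four groups.

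Neither analysis has a covariate, a matched-set structure, or a role for EtCO2 or BP.

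Control of confounding is by design. The synopsis describes "age-, gender- and blood pressure (BP)-matched healthy control (HC) subjects", and Sections 4, 5.1, 5.2, 7.1 and 7.2 say the same in substance. A second sentence in Section 7.2 lists age, gender and medical co-morbidities instead. Section 7.1 plans 11 analysable participants in each of the four groups. Section 7.3 admits ages 18 to 100, and Section 7.4 excludes several major co-morbidities.

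On carbon dioxide, Section 4 states "Cerebral blood flow (CBF) is also strongly influenced by the arterial partial pressure of carbon dioxide" and "CA is improved by hypocapnia and impaired by hypercapnia". It mentions time-domain information "from the analysis of mean BP, CBFv, heart rate (HR) and end-tidal partial pressure of carbon dioxide", but only as background. Section 8.4 records beat-to-beat BP and EtCO2 together with CBFv. Section 15.2 says only that the recordings feed later analyses.

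**The concern.** The primary objective is a comparison between groups in an observational case-control study. If the groups differ in age or sex, and these affect CBFv, ARI or the response to the task, part of an apparent disease difference may not be due to disease. The planned baseline comparison can reveal an imbalance but does not correct for it.

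There is a second, smaller gap. Matching on resting BP says nothing about changes in BP or CO2 while a participant speaks and works through the ACE-III. If such changes differ between groups, a difference in CBFv response could be misread as altered neurovascular coupling. The signals needed to examine this are recorded, but Section 11.1 specifies no use of them.

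**Working it through.** **1. What matching covers.** Four groups give six pairwise contrasts: three patient-versus-control and three patient-versus-patient. Matching is stated for controls against patients only. With 11 controls and 33 patients, 1:1 matching reaches at most 11/33, one third, of the patients. No ratio, caliper or procedure is given. The three patient-versus-patient contrasts have no matching.

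**2. The plan's own figure.** Section 11.2 says 11 per group will detect "a difference between groups (MCI patients, VascD patients, AlzD patients and HC subjects) in the ARI of 2 units with 80% power" at the 5% level, and also that a formal calculation was not possible. The SD of ARI is not given, so the figure can be neither confirmed nor refuted. It can only be solved backwards. For a two-sided 5% test with 80% power and standard error SD × √(2/11):

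- two-sample t, df 20: detectable difference 1.256 SD, so SD = 2/1.256 = 1.59;
- pooled error from four groups, df 40: 1.224 SD, so SD = 2/1.224 = 1.63.

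**3. Baseline ARI contrast (assumed shifts).** With SD 1.59 and df 20, suppose confounding moves one contrast by 0.25, 0.5 or 1.0 ARI unit, that is 0.157, 0.314 or 0.628 SD. The false-positive rate per comparison is then:

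| Bonferroni for | Nominal | 0.25 unit | 0.5 unit | 1.0 unit |
|---|---|---|---|---|
| 3 contrasts | 1.7% | 2.3% | 4.5% | 15.3% |
| 6 contrasts | 0.8% | 1.2% | 2.5% | 9.9% |

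**4. Group-by-task test (assumed inputs).** Simplify the task effect to one change score per person with SD 1. Let two of the four groups be older by g SD, and let age correlate r with the change. Those two group means move by δ = g × r, and the noncentrality is 11 × 4 × (δ/2)² = 11δ². The test is F(3,40) at 5%.

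| g | r | δ | 11δ² | Rejection, no disease effect |
|---|---|---|---|---|
| 0.5 | 0.2 | 0.1 | 0.11 | 5.6% |
| 0.5 | 0.4 | 0.2 | 0.44 | 7.5% |
| 1.0 | 0.2 | 0.2 | 0.44 | 7.5% |
| 1.0 | 0.4 | 0.4 | 1.76 | 16.1% |

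In simulations of the same four cases (12,000 each), ANCOVA on the change with age and sex rejects 4.9% to 5.1% of the time. That follows from the set-up: age is the only confounder and enters in the correct form.

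**5. Why a covariate main effect is not enough.** In simulated data with four task levels, removing an age effect that is constant within each person leaves the group-by-task F unchanged, at 1.1558 on (9,120) df. Only a covariate-by-task term, or ANCOVA on the change, alters that test. With both such terms the df are (9,114).

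**6. Cost of two covariates that explain nothing.** Between-subject error df fall from 40 to 38. The variance factor is 1 + 2/(44 − 4 − 2 − 1) = 1.054, so the standard error rises by a factor of 1.027. Detectable differences at 80% power are:

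| Two-sided level | In SD | In ARI units (SD 1.63) |
|---|---|---|
| 5% | 1.22 to 1.26 | 2.00 to 2.06 |
| 5%/3 | 1.43 to 1.47 | 2.34 to 2.41 |
| 5%/6 | 1.55 to 1.60 | 2.54 to 2.61 |

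Precision improves once the covariates explain more than about 5% to 6% of the residual variance. For a contrast whose groups differ by 1 SD in age, the standard error is √[(2/11 + 1/40)/(2/11)] = 1.07 times as large.

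**The case against.** The best defence is that the main confounders are handled by design. Controls are matched on age, gender and BP, and Section 7.4 excludes severe respiratory disease, carotid stenosis, atrial fibrillation and severe cardiac failure. This stands for the patient-versus-control contrasts: age gaps of 0.5 to 1 SD there would mean that matching had largely failed. It does not reach the patient-versus-patient contrasts.

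Second, Section 6.2 expresses the CBFv response as a percentage change, so an influence that scales a person's velocity equally at rest and on task cancels out. That also stands. Bias in the group-by-task test requires age or sex to alter the task response itself, and no section says that they do.

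Third, the error rates assume the confounding that they illustrate, and at the mild end the inflation is trivial (5.6% against 5%). This is correct. A reader might infer that the trial's false-positive rate is 16%; the documents support no such figure.

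Fourth, a reader might infer that EtCO2 and BP are ignored, or that EtCO2 belongs in the main model. Neither follows. Section 15.2 leaves later analyses open, and the baseline tests could include resting values, so the accurate statement is that no task-related analysis is specified. Leaving EtCO2 out of the main model is defensible, because adjustment could remove part of a genuine task response.

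Fifth, resting BP is a stated matching factor but is not among the proposed covariates. That is a fair query; the set is kept to two because 44 participants can carry only a few.

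Finally, the two matching lists in Section 7.2 may be cumulative rather than contradictory, so that point is editorial.

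**Conclusion.** The concern holds in a limited form. Section 11.1 leaves the between-group comparisons of CBFv and ARI unadjusted. Matching gives partial control of the patient-versus-control contrasts and none of the contrasts among MCI, VascD and AlzD. It would be wrong to read this as a study without control of confounding.

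The actual bias cannot be computed from the documents. The 5.6% to 16.1% range depends on assumed age gaps and correlations, a single change score, and two groups shifted together; it bears mainly on the unmatched contrasts. The case for change rests on the low cost of adjustment with data already collected, and on the greater credibility of covariates chosen before the data are seen. This is an improvement the sponsor should make, not a flaw that invalidates the design. The EtCO2 and BP element is supplementary.

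**What to change.** In Section 11.1:

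- Use ANCOVA with age and sex for baseline CBFv and ARI; where normality fails, use a transformed or rank-based version.
- For the ACE-III effect, add age-by-task and sex-by-task terms to the repeated measures model, or use ANCOVA on the task-related change.
- As a supplement, compare task-related EtCO2 and BP change between groups. Pre-specify a sensitivity analysis of the CBFv response adjusted for both over the same recording segments, reported beside the unadjusted result. For ARI, adjust for EtCO2 only, since ARI is itself derived from the relation between BP and CBFv.
- State that age and sex adjustment does not remove confounding by co-morbidity, medication or education.

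In Section 7.2, say how 11 controls are matched to 33 patients, and reconcile BP with medical co-morbidities as matching factors, there and wherever the matching is described.

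The cost is a wording amendment, with approval under Section 14.5 if substantial. No new data are needed. The statistical price is two between-subject degrees of freedom and the roughly 3% loss worked out above. Within-subject error df fall from 120 to 114 if the model has a baseline and three task recordings; Section 11.1 does not define the levels, and the amendment should.

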### **11.2 Sample size calculation**

A formal sample size calculation was not possible for this study therefore a realistic number of participants has been selected based on previous experience of similar research studies by [name], [name] and [name].

However, to detect a change of 2 units in autoregulation Index (ARI) and to calculate the required sample size we followed the technique as previously described by others (Brodie FG et al, 2009). For this study a sample of 11 patients per intervention group will allow the detection of a difference between groups (MCI patients, VascD patients, AlzD patients and HC subjects) in the ARI of 2 units with 80% power at the 5% significance level.

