### **6.2 Primary and Secondary Endpoints/Outcome Measures**

This is not an intervention study, and therefore it would not be appropriate to assess the classical primary and secondary outcome measures such as death and disability for this study. However, we intend to evaluate the following relevant outcomes:

- 1) The percentage of recruited subjects (HC, MCI patients, VascD patients and AlzD patients) able to comply with the full measurement protocol.
- 2) The percentage of measurements rejected because of aspects related to data quality during the analysis protocol, with recorded reasons.
- 3) Overall, the percentage of recruited subjects (healthy controls, MCI patients, VascD patients and AlzD patients) in whom values for the following parameters can be derived:
  - % change of CBFv at baseline in response to performance of the ACE-III Cognitive Examination
  - Autoregulation index (using the Tiecks model and from the phase, gain and coherence).

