## **8.2 TCD window insonation check**

Once a consent form has been signed, and before collecting baseline information on demographics, medical history, medications, and handedness, participants will undergo a brief Transcranial Doppler Ultrasound (TCD) check to ensure they have adequate acoustic temporal windows (inadequacy rates of 5-37% well documented in the literature) [Itoh et al 1993, Bos et al 2007, Marinoni et al 1997].

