## **8.3 Collection of demographic data**

Baseline demographic data will be collected from the participants as detailed below:

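### Does the 80% power for a 2-unit ARI difference fail because the group comparisons are Bonferroni-corrected?

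*Combined protocol and SAP*

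**What the plan says.** Section 11.2 (Sample size calculation) opens by saying that no formal calculation could be made and that a realistic number was taken from experience with similar studies. It then says that 11 per group allows detection of a difference between the four groups "in the ARI of 2 units with 80% power at the 5% significance level". For the method it cites a study of the reliability of autoregulation measurement. It gives no SD, test, sidedness or number of comparisons.

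Section 11.1 (Statistical analysis) contains two between-group procedures:

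- "Comparison between baseline data for MCI patients, VascD patients, AlzD patients and HC will be made using Student t-tests" or a non-parametric alternative, "with Bonferroni correction applied to multiple comparisons". The variables are not listed and the number of comparisons is not given.
- "Repeated measures ANOVA will be adopted to test for the effect of performance of the ACE-III Cognitive Examination on CBFv and ARI", across the same four groups. This sentence has no Bonferroni wording.

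The null hypothesis in 11.1 covers "cerebral haemodynamic parameters, including CBFv and ARI, and any alterations related to the performance of the ACE-III Cognitive Examination". ARI belongs to secondary objective 1 (section 5.2). The primary objective (section 5.1) concerns cerebral blood flow velocity (CBFv).

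**The concern.** The power is quoted at an unadjusted 5% level, whereas the t-tests in 11.1 run at 5% divided by the number of comparisons. With four groups that number is three (each patient group against controls) or six (all pairs). If those t-tests include baseline ARI, the level in 11.2 is not the level that will be applied, and power at the applied level is lower.

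There is some reason to think that baseline ARI is included. The null hypothesis names ARI separately from its changes during the ACE-III. Section 8.4 calls the 5-minute resting recording a baseline, and section 6.2 refers to "change of CBFv at baseline in response to performance of the ACE-III Cognitive Examination". Apart from the ANOVA, the t-tests are the only between-group test in 11.1.

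At stake is how a negative result is read. The 80% sentence is the only quantitative support for 11 per group. A non-significant baseline ARI comparison in a 44-person study might be taken as stronger evidence of no difference than it is.

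**Working it through.** **Inputs from section 11.2.** n = 11 per group, difference 2 ARI units, power 80%, level 5%. The SD, test and sidedness are not given, so the 80% cannot be reproduced independently. It can only be back-solved for an assumed test.

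**Step 1: SD implied by one two-sided two-sample t-test (assumption).** Power is P(|T| > t_crit), with T noncentral t on 2n − 2 = 20 df and noncentrality d√(n/2). At two-sided 0.05, t_crit = 2.086. Power of 80% requires d = 1.256, so noncentrality = 1.256 × √5.5 = 2.945 and SD = 2/1.256 = 1.59.

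**Step 2: the same d at corrected levels.**

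| Level | t_crit (20 df) | Power for a given pair |
|---|---|---|
| 0.05 | 2.086 | 80.0% |
| 0.05/3 | 2.613 | 63.3% |
| 0.05/6 | 2.927 | 52.1% |

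Simulation of 400,000 trials gives 79.9%, 63.1% and 52.1%. At this SD, 80% corrected power would take 15 per group (80.7%) for three comparisons or 18 (82.5%) for six. With 11 per group, corrected power is at least 80% only if the SD is at most 1.34 (three) or 1.23 (six).

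**Step 3: the test that names ARI.** Power of the repeated measures ANOVA itself cannot be computed, because the within-subject correlation and the number of repeated measures per subject are not given. As a rough stand-in, take a one-way four-group F-test on 3 and 40 df at 5% (critical value 2.839), with noncentrality λ = 11 × Σ(μᵢ − μ̄)²/SD² and SD² = 1.592² = 2.536. The largest gap between means is 2 units throughout.

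| Means | Σ(μᵢ − μ̄)² | λ | Power at 5% |
|---|---|---|---|
| 0, 1, 1, 2 | 2 | 8.68 | 65% |
| 0, 0, 0, 2 | 3 | 13.01 | 83% |
| 0, 0, 2, 2 | 4 | 17.35 | 93% |

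The first and last rows are the extremes for a largest gap of 2. The stated 80% lies inside this range.

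**Step 4: other routes to the 80%.** If the 80% came instead from an F-test at n = 11, the implied SD is 1.35, 1.66 or 1.91 for the three patterns. Corrected pairwise t-test power is then 79%, 59% or 45% for three comparisons and 70%, 48% or 35% for six. With no correction at all it would be 91%, 77% or 65%, so part of the distance from 80% on this route has nothing to do with Bonferroni.

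**Step 5: does the correction reach ARI?** The uses of the word baseline differ:

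- Section 8.2: "baseline information on demographics, medical history, medications, and handedness".
- Section 8.3: "Baseline demographic data will be collected from the participants as detailed below".
- Sections 6.2 and 8.4: resting velocity and resting recordings.

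The closest match in wording to the phrase in 11.1 is section 8.3, on demographics. No section calls ARI baseline data. A check that the groups are comparable is also a natural purpose for such t-tests in a study with matched controls (sections 7.1 and 7.2).

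**The case for a change.** The strongest case for acting is that the text is incomplete on either reading. If baseline ARI is in the corrected family, the 5% in 11.2 is not the level used. If it is not, ARI is tested only by the ANOVA, and 11.2 does not say that its 80% refers to that test. A few sentences would settle the matter, without extra participants or altered tests. The opening of 11.2 also sits awkwardly with the calculation that follows it.

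The incompleteness stands: 11.2 does not link its power to a test, and 11.1 does not define the corrected family. What does not stand is the step from there to an overstated power. A repeated measures ANOVA with group as a between-subject factor also gives a group effect on ARI, so the first part of the null hypothesis does not need baseline t-tests. Secondary objective 1 asks whether ARI differs between groups with ACE-III performance, which is the ANOVA's question. The missing inputs may also be in the cited reliability study, which was not available here; leaving them out of the text is no evidence against the figure.

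**Conclusion.** The concern does not call for a change. The figures of 63% and 52% are arithmetically sound, but they rest on two assumptions that the documents do not establish: that the 80% was derived from one two-sided t-test (implied SD 1.59, back-solved and not a document figure), and that baseline ARI is in the Bonferroni-corrected set. On the reading closest to the text, ARI is tested by the ANOVA at 5%. There the stated 80% is plausible, within about 65% to 93% for the simple F-test stand-in at the same SD.

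What is left is unwritten detail that analysts can settle sensibly. They run the ANOVA on ARI at 5%. If they also compare resting ARI pairwise, they apply the correction already written in 11.1 and do not attach the 80% to those tests. Every test stays the same, and so does the group size, which 11.2 attributes first to feasibility. The primary CBFv comparison never relied on this figure. The only residual risk is over-reading a negative pairwise result for a secondary parameter, and the size of that risk cannot be fixed without the SD.
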